Protocol Signature Page

Tracking Renal Tumors After Cryoablation Evaluation (TRACE)

Protocol Number CUC10-RNL02-03

Study Design Registry

Date 20 May 2011

Galil Protocol Approval

We, the undersigned, have read and approve the protocol specified above and agree on its content.

[name], MSN
Director, Clinical Research

Signature

[name]
Director, Regulatory Affairs

Signature

Investigator Signature

I, the undersigned, have read and understand the protocol specified above and agree on its content. I agree to perform and conduct the registry as described in the protocol.

Printed Name

Signature

Date

Protocol Title: Tracking Renal Tumors After Cryoablation Evaluation (TRACE)

Sponsor: Galil Medical
[name]
[name]

Registry Responsibility: [name], MSN
Director, Clinical Research
Galil Medical
[name]
[name]

Date of Issue: 20 May 2011

Protocol Number: CUC10-RNL02-03

This protocol contains confidential information for use by the Investigators and their designated representatives participating in this Registry. It should be held confidential and maintained in a secure location.

Do not copy or distribute without written permission.

Protocol Synopsis

Tracking Renal Tumors After Cryoablation Evaluation (TRACE)

Protocol Number	CUC10-RNL02-03
Objectives	
The primary objective of the study is to assess the short- and long-term outcomes of subjects who undergo renal lesion ablation via cryotherapy with products offered by Galil Medical. Secondary objectives are:
 
 • An assessment of outcomes across laparoscopic-assisted, percutaneous and open cryoablation procedures • Characterization of standards of care for cryoablation procedure follow-up across the participating registry centers
Registry Design	An observational, open-label, single-arm, multi-center study of subjects who have undergone renal lesion cryoablation per their physician's standard of care
Registry Device	The study will include subjects who have undergone cryoablation via a Galil Medical cryoablation system using Galil Medical needles
Control Device	Not applicable
Number of Sites	Approximately 10 sites in the United States are anticipated to participate; a mix of academic and community centers
Number of Subjects	Approximately 250 subjects are anticipated to be enrolled
Registry Methodology	Patients with a renal lesion suspicious for malignancy pre-operatively who have been determined to be an appropriate candidate for cryoablation will be offered enrollment into the registry. Patients agreeing to participate will read and sign an informed consent form. Participation in the registry will not influence direct subject treatment procedures or follow-up care schedule. Each physician will manage their enrolled subjects as per their individual standard of care and provide data regarding each subject as they are seen. Baseline and follow-up data will be collected for each subject via a web-based electronic data collection tool.
Randomization	Not applicable

Procedural Measures	
Cryosurgery parameters will include:
 
 • Procedure method (open, laparoscopic, percutaneous) • Number of lesions treated with cryoablation • Type of hemostatic agents or maneuvers used • Lesion size • Lesion location • Number and type of cryosurgery needles used • Number of freeze and thaw cycles • Freeze and thaw times, per cycle • Hilar clamping • Embolization • Galil needle cautery • Method of thaw (active or passive) • Method of monitoring iceball formation (US, CT, MRI) • Involvement of the kidney's collecting system • Post-operative HCT
Safety Measures	
Primary safety parameters will include:
 
 • Evaluation of cryosurgery-related adverse events
Outcome Measures	
Outcome parameters will include:
 
 • Changes in lesion size • Renal function status as determined by estimated Glomerular Filtration Rate • Length of hospital stay • Post-cryoablation lesion enhancement • Post-cryoablation biopsy (if performed) • Disease recurrence or progression • Disease-specific survival rates • Overall survival rates and times • Quality of Life assessment • Emergence of new neoplastic disease (any type) • Development of metastatic disease
Follow-Up Schedule	Planned per-subject follow-up is 5 years

Inclusion Criteria	
 1. Patient is at least 18 years of age. 2. Renal lesion suspicious for malignancy. 3. Patient is to undergo renal lesion cryoablation via a Galil Medical cryoablation system using Galil Medical needles for treatment of primary or recurrent disease. 4. Patient is to be available for long-term follow-up per the enrolling physician's standard care practices. 5. Patient has provided written informed consent.
Key Exclusion Criteria	
 1. Patient is either currently using or has used within the last 30 days an investigational product of any type. 2. Patient has metastatic disease to or from the kidney. 3. Patient has had previous therapy on the index lesion (e.g. radiofrequency, cryoablation, partial nephrectomy).
Renal Lesion Size Criteria	While there are no strict exclusion criteria with regard to lesion size, the typical renal lesion suitable for cryoablation is ≤ 4 cm. Physicians are to use their training and experience to determine the size of a renal lesion that is appropriate for cryoablation.
Statistical Methods	
Continuous variables (e.g., age) will be summarized by the number of subjects, mean, standard deviation, median, minimum and maximum. Categorical variables (e.g., race) will be summarized by frequencies and percentages of subjects in each category.
 
Reporting from the database will include:
 
 • Baseline demographics and disease status will be summarized. • Disease recurrence or progression will be summarized. • Survival and disease-specific survival rates will be summarized at given time points. • Overall survival (time to death) disease-specific survival (time to death of kidney cancer), and recurrence free survival (time to disease recurrence or progression) will be analyzed using the Kaplan-Meier methodology and presented graphically. • Follow-up patterns across physicians/centers will be summarized. • Lesion size reduction will be analyzed. • Relative efficacy in subject subgroups may be explored.

Table of Contents

Protocol Synopsis	iii
Table of Contents	vi
1. Background	1
1.1. Cryotherapy	1
1.2. Cryo-Technology	1
2. Device Description	1
2.1. Cryotherapy Systems	1
3. Registry Rationale	2
4. Registry Objectives	2
5. Registry Design	3
5.1. Description of the Registry	3
6. Registry Population	4
6.1. Subject Enrollment	4
6.2. Inclusion Criteria	4
6.3. Exclusion Criteria	4
6.4. Renal Lesion Size	5
6.5. Withdrawal of Subjects	5
7. Registry Assessments	6
7.1. Pre-Cryoablation Evaluation	7
7.2. Cryoablation Procedure	8
7.3. Early Complications	9
7.4. First Post-Operative Follow-Up	9
7.5. Ongoing Follow-Up Visits	9
7.6. Withdrawal	9
8. Statistical Methods	10
8.1. Sample Size Estimate and Justification	10
8.2. Missing Data	10
8.3. Analysis Populations	10
8.4. Measures	10
8.5. Analyses	12
9. Data Management	13
9.1. Data Collection	13
9.2. Data Processing	13

1.1. Cryotherapy

Cryosurgery is a safe, well-established FDA-cleared technology that has been successfully applied for selective ablation and treatment of different kinds of benign and malignant conditions, such as: prostate and renal cancer, liver lesions, soft tissue lesions, fibroadenoma of breast, ear-nose and throat applications, thoracic applications (atrial fibrillation, pulmonary lesions), cryoanalgesia, dermatology, as well as pre-cancerous lesions of the cervix. Galil Medical has developed a range of products based on its cryotherapy platform and incorporating updated freezing technology and needle design. The company's core technology is a significant advance in cryoablative treatment of renal and other lesions.

1.2. Cryo-Technology

Modern cryoablation dates back to 1961, when automated cryosurgical units that pump liquid nitrogen through the tip of the cryoprobe were introduced.¹ This innovation led to the investigation of cryoablation for different diseases, but cumbersome cryoprobes and a lack of control over the freezing process made widespread use impractical. The resurgence in interest in cryoablation results from the introduction of modern cryoprobes, which exploit the Joule–Thomson (J–T) effect.² The J–T effect predicts changes in temperature as gases expand through narrow ports from high to low pressure. This is a constant enthalpy expansion that, in the case of argon gas, results in rapid cooling to the boiling point of argon (-186°C). To accomplish this, high-pressure (3,000 psi) ambient-temperature argon gas is circulated to the cryoprobe tip where it expands rapidly as it drops to room pressure. Under the J–T effect, some gases - such as helium - warm up rather than cool when expanded. Accordingly, helium can and has been incorporated into cryogenic systems to rapidly warm the cryoprobe in order to arrest the freezing process or thaw the iceball. The flow of argon and helium is controlled by computer-modulated gas regulators. The temperatures of cryoprobes controlled by gas systems are finely adjustable and respond within seconds to user input. (By comparison, liquid nitrogen systems have a lag time of up to 2 minutes.)^{3,4} The expanded gases are circulated back to the cryogenic unit through the larger outer lumen of the cryoprobe and the supply hose. The venting of used gas, usually into the room, occurs at the cryogenic machine. Both argon and helium are inert gases, making such venting harmless.

2. Device Description

2.1. Cryotherapy Systems

The cryo-technology developed by Galil Medical, Ltd. (Yokneam, Israel) is based on Joule–Thomson effect, and utilizes Argon gas for freezing. Passive thaw, helium gas thaw or electric thaw may be used.

This registry will utilize Galil Medical's commercially available needles and thermal sensors. Each cryogenic needle forms a different shape and size of iceball. Multiple cryogenic needles can be operated simultaneously. Thus, insertion of several cryogenic needles into the lesion, or even into 2 or 3 lesions concomitantly significantly shortens the length of treatment, and provides flexibility in treating lesions of varying sizes by matching the cryoablation needle number and configuration for a specific lesion. Tissue thermal sensors enable the real-time tissue temperature monitoring, thus contribute to the safety and effectiveness of the procedure.

Galil Medical's commercially available cryotherapy systems and associated needles are FDA cleared for use as a cryosurgical tool in the fields of general surgery, dermatology, neurology (including cryoanalgesia), thoracic surgery, ear-nose and throat (ENT), gynecology, oncology, proctology and urology. These systems are designed to destroy tissue (including prostate and kidney tissue, liver metastases, tumors, skin lesions and warts) by the application of extremely cold temperatures. Cryoablation procedures using Galil's systems may be performed under the guidance of ultrasound, CT or MRI. During the last eight years, thousands of cryoablation procedures have been safely and effectively performed with Galil's cryoablation equipment, primarily for the treatment of prostate and kidney cancers, as well other applications.

3. Registry Rationale

The data generated by the registry database will evaluate the use, safety and effectiveness of cryotherapy for renal lesions and will assess the potential advantages and disadvantages of the procedure (e.g., disease recurrence or progression, disease-specific survival rates, overall survival rates, etc.). It will also be used to facilitate long-term surveillance of subjects undergoing renal lesion cryoablation. In addition, the registry may be used as a continuous quality improvement tool on behalf of the treating physicians and will contribute to the development and refinement of standards of care.

4. Registry Objectives

The primary objective of the registry is to assess the short- and long-term outcomes of subjects who undergo renal lesion ablation via cryotherapy with products offered by Galil Medical.

Secondary objectives are:

- An assessment of outcomes across laparoscopic-assisted, percutaneous and open cryoablation procedures.
- Characterization of standards of care for cryoablation procedure follow-up across the participating registry centers.

5. Registry Design

5.1. Description of the Registry

TRACE is an observational, open-label, single-arm, multi-center registry of subjects who have undergone renal lesion cryoablation per their physician's standard of care. Patients 18 years of age or older who have been determined to be an appropriate candidate for cryoablation will be offered enrollment into the registry. Subjects will be recruited from a variety of practice settings, including academic centers and community-based physicians. Those agreeing to participate in the registry will read and sign an informed consent form prior to their cryoablation procedure. Subjects will be observed for five years from the date of their cryoablation procedure.

The registry is non-interventional; it will neither direct the cryoablation procedures performed nor define the post-surgery follow-up of each subject. A subject's participation in the registry will not influence or direct subject treatment procedures or follow-up care. Physicians will use their discretion and personal standards of care to select subjects, perform the cryoablation procedures and define appropriate follow-up visit schedules for their subjects; it is anticipated that subjects will be seen at least once per year during the five-year follow-up period of TRACE. Subjects may be followed by the physician performing the cryoablation procedure or by their local/personal physician. The enrolling physician will be responsible for providing the follow-up data to the registry and will, as appropriate, work with a subject's local/personal physician to collect the follow-up data.

A subject's Pre-surgery/Enrollment visit will include the collection of general demographics information, a brief medical history (general and renal specific), comorbidities, diagnosis details (imaging, biopsy) and current classes of medications. Subjects will be asked to complete a pre-surgery quality of life (SF-12) questionnaire. At the cryoablation visit, details of the cryotherapy procedure will be collected, as well as any potentially or directly related adverse events.

At the first post-cryoablation visit, data regarding initial outcomes and potentially or directly related complications, as applicable, will be collected, as will details regarding any post-operative interventional treatments. Data collection for subsequent follow-up visits will address delayed potentially or directly related complications, ongoing imaging and biopsy procedures as well as the introduction and continued use of new cancer treatments.

The schedule and number of follow-up visits for each subject will be determined by his/her physician's standard of care. Within this context, semi-annual to annual follow-up during the five-year follow-up period is generally anticipated though it is recognized that follow-up schedules will vary among enrolled subjects. The subject will be asked to complete the quality of life questionnaire post-cryoablation at the 6 and 12 month follow-up intervals if scheduled.

All potentially related and directly related cryoablation adverse events (AEs), serious adverse events (SAEs) and unanticipated adverse device effects (UADEs) that occur within 30 days after

the cryoablation procedure is performed will be recorded. The cryoablation AEs, SAEs, and UADEs identified within the first 30 days after the cryoablation procedure will be followed and reported until resolution or for a period of 6 months.

Concomitant medications may be prescribed as per the physician's standard of care while the subject is participating in the registry. Only classes of concomitant medications will be collected at each follow-up visit.

6. Registry Population

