4 STUDY DESIGN

4.1 General Design

This is an observational, open-label, single-arm, multi-center study of patients who have undergone renal lesion cryoablation per their physician's standard of care via a Galil Medical cryoablation system using Galil Medical needles.

Data for patients who agree to participate are collected prospectively. (i.e., registry data collection).

TRACE is anticipated to enroll approximately 250 patients at approximately 10 sites.

Patients will be enrolled from a mix of academic and community-based sites.

The schedule and number of follow-up visits for each patient will be determined by his/her physician's standard of care.

Within this context, semi-annual to annual follow-up during the five-year follow-up period is anticipated though it is recognized that follow-up schedules will vary among enrolled patients. Planned per-patient follow-up is 5 years.

The results generated by the registry database will evaluate the use, safety and effectiveness of cryotherapy for renal lesions and will assess the potential advantages and disadvantages of the procedure (e.g., disease recurrence or progression, disease-specific survival rates, overall survival rates, etc).

It will also provide information on long-term surveillance of patients undergoing renal lesion cryoablation.

In addition, this registry may be used as a continuous quality improvement tool on behalf of the treating physicians and will contribute to the development and refinement of standards of care for treatment and follow-up assessments.

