6.4.4 Disease recurrence

Time to recurrence (TTR) is defined as the time from date of cryoprocedure to disease recurrence with enhancement in at least one lesion. A lesion is considered to have disease recurrence if the response to the question “What is the status of the lesion?” in the follow-up lesion assessment eCRF page, is “Recurrent”, and there is a “Yes” response to the related question, “If Progressing or recurrent, was the lesion identified by contrast enhancement?”

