6.5 Safety Assessments

6.5.1 Procedural and intra-operative data

The following will be included in the presentation of procedural and intra-operative data:

- Procedure method (i.e., the response to the question “What was the surgical approach?” in the eCRF)
- Surgical approach type
- Type of Galil Medical cryoablation system used (i.e., the response to the field “Type of cryotherapy system used on patient” in the eCRF)
- Method of monitoring used to place cryoablation needles
- Method of monitoring iceball formation
- Completion of cryotherapy
- Who performed the procedure?
- Type of anesthesia used
- Total anesthesia time
- Estimated blood loss during procedure
- Total duration of operation
- Type of hemostatic agents or maneuvers used
- Number of lesions identified at baseline but not treated with cryoablation
- Number of lesions treated with cryoablation
- Number and type of cryosurgery needles used
- Number of freeze and thaw cycles
- Total freeze time over all cycles; i.e., the sum of the times recorded in the eCRF fields: “Duration of active freeze”
- Total thaw time over all cycles; i.e., the sum of the times recorded in the eCRF fields: “Duration of thaw”
- Lowest temperature achieved at end of all freeze cycles, separately for temperature at the center and at the periphery
- Lesion in right or left kidney?
- Hilar clamping performed?
- Method of thaw
- Was embolization performed prior to cryoblation?
- Involvement of the kidney’s collecting system, according to the following fields on the eCRF:
 - Did the iceball appear to touch the collection system?

- Did the iceball appear to involve (engulf) the collection system?
- Was there evidence for new gross hematuria during the course of the procedure potentially due to involvement of the iceball with the collecting system?
- Post-operative hematocrit (HCT)
- Were other surgical procedures performed during the patient's hospital stay?
- Was an extended hospital stay needed due to an adjunct procedure?
- Achievement of technical success at first post-cryoablation imaging assessment

Time from initial diagnosis of the suspicious renal mass to the date of cryoprocedure will be calculated as follows:

Time from diagnosis of suspicious renal mass (in months) =

$$(\text{Date of cryoprocedure} - \text{Date of diagnosis} + 1)/30.4375.$$

Length of hospital stay (in hours) will be computed using the discharge date and time and the admission date and time recorded on the eCRF.

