A patient will be considered to have achieved technical success at first post-cryoablation imaging assessment according to the table below. NB: if any one of the three eCRF fields in the table below have missing data then technical success will also be set to missing.

eCRF field: Was cryotherapy completed?	eCRF field: What is the status of this lesion? (at first post- cryoablation imaging assessment)	eCRF field: If progressing or recurrent, was the lesion identified by contrast enhancement? (at first post-cryoablation imaging assessment)	Derivation of technical success (at first post- cryoablation imaging assessment)
“Yes”	“No longer present”, “Smaller”, or “Stable or no change”	This field should not be completed	“Yes”
“Yes”	“Progressing”, or “Recurrent”	“No”	“Yes”
“Yes” or “No”	“Progressing”, or “Recurrent”	“Yes”	“No”

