8.7.1 Procedural and intra-operative data

The following procedural and intra-operative data will be summarized using descriptive statistics, or as a number and percentage for categorical data.

The following data will be summarized in a per-patient analysis:

- Procedure method (open, laparoscopic, percutaneous); this data will also be summarized by site, and also by NS complexity categories at baseline
- Surgical approach type (not applicable, transperitoneal, retroperitoneal, hand-assisted, single port, natural orifice transluminal endoscopic surgery [NOTES], other)
- Type of Galil Medical cryoablation system used (SeedNet, Presice, Visual-Ice)
- Method of monitoring used to place cryoablation needles (CT, MRI, ultrasound)
- Method of monitoring iceball formation (CT, MRI, ultrasound)
- Completion of cryotherapy (yes, no)
- Achievement of technical success at first post-cryoablation imaging assessment (yes, no)
- Who performed the procedure? (interventional radiologist [IR], urologist, IR and urologist together, other); this data will also be summarized by site
- Type of anesthesia used (general, regional, local only, conscious); this data will also be summarized by site
- Total anesthesia time (in minutes)
- Estimated blood loss during procedure (in cc)
- Total duration of operation (in minutes); this data will also be summarized by NS complexity categories at baseline
- Type of hemostatic agents or maneuvers used (none, compression, suturing, Floseal, Gelfoam, Surgicel, other)
- Number of lesions identified at baseline but not treated with cryoablation (categorical)
 - Note: the data should only be taken from the first (date) Follow-up Lesion Assessment for each subject
- Number of lesions treated with cryoablation (categorical)
- Number of freeze and thaw cycles; this data will also be summarized by NS complexity categories at baseline
- Involvement of the kidney's collecting system, according to the following fields on the eCRF:
 - Did the iceball appear to touch the collection system? (yes, no)
 - Did the iceball appear to involve (engulf) the collection system? (yes, no)
 - Was there evidence for new gross hematuria during the course of the procedure potentially due to involvement of the iceball with the collecting system? (yes, no)
- Post-operative hematocrit (in %)

- Time from initial diagnosis of the suspicious renal mass to the date of cryoprocedure (in months)
- Length of hospital stay (in hours)

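### Technical success is read from the first follow-up scan with no time limit, so a late first scan can count a later recurrence as a procedural failure and the pooled rate depends on scan timing.

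*Protocol*

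**What the plan says.** **Definition.** SAP 6.5.1 lists technical success among the procedural and intra-operative data and states: "A patient will be considered to have achieved technical success at first post-cryoablation imaging assessment according to the table below". The table uses three eCRF fields: whether cryotherapy was completed, lesion status, and, for a progressing or recurrent lesion, whether contrast enhancement identified it. Its last row makes an enhancing lesion rated Progressing or Recurrent a failure. Without enhancement, and with cryotherapy completed, the same ratings give a success. No latest date is set for the scan, and the definition is not linked to the analysis windows in SAP 6.2.2 (Pre 6 Month, days 1–92; 6 Month, days 93–275; 12 Month, days 276–549; and so on).

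**Scan timing.** Protocol 5.1 says of the registry that "it will neither direct the cryoablation procedures performed nor define the post-surgery follow-up of each subject", and expects that "semi-annual to annual follow-up during the five-year follow-up period is generally anticipated though it is recognized that follow-up schedules will vary among enrolled subjects". SAP 4.1 agrees: "The schedule and number of follow-up visits for each patient will be determined by his/her physician's standard of care". Protocol 7.4 lists adverse events and surgical interventions for the first post-operative follow-up, but not imaging. Imaging results first appear in Protocol 7.5, to be collected when available, at visits anticipated at least yearly.

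**Reporting.** SAP 8.7.1 summarises technical success as one per-patient yes/no item. Procedure method, operator and anesthesia in the same list are also shown by site; technical success is not.

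**The concern.** Technical success is meant to describe the procedure: was the lesion fully ablated? A scan in the first weeks mostly answers that. A first scan at a year answers a different question, whether the lesion was fully ablated and has stayed free of enhancing regrowth since. The derivation table treats the two scans alike, and nothing in it separates incomplete ablation from recurrence after complete ablation.

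The reported percentage therefore mixes the two in a proportion set by follow-up habits. A reader who takes it as a measure of procedural quality, or sets it beside a rate from a series with an early protocol scan, may be misled.

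**Working it through.** **1. Is there a figure to reproduce?** No. The documents give no expected technical success rate, no target and no recurrence rate, and SAP 4.4 states that no power calculation was done. The defect is established by reading; its size can only be illustrated.

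**2. The rule applied to one patient.** Suppose ablation is complete and an enhancing lesion appears at month 10.
- First scan at month 3, with the lesion stable: technical success. The month-12 scan then records a recurrence.
- First scan at month 12, with the lesion rated Recurrent and enhancing: technical failure.

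The procedure and the disease course are the same; only the date of the first scan differs. A yearly first scan is within what Protocol 5.1 and 7.5 anticipate.

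**3. Illustration of size.** Let p be the proportion with truly incomplete ablation, h the yearly hazard of later enhancing recurrence or progression, and t the time of the first scan in years. Then

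apparent failure(t) = 1 − (1 − p) × exp(−h × t).

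The values of p and h (2% or 5% each) are assumptions and are not in the documents. For p = 2% and h = 5%:
- 3 months: 1 − 0.98 × exp(−0.0125) = 3.22%
- 12 months: 1 − 0.98 × exp(−0.05) = 6.78%
- difference: 3.56 points

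| p | h per year | Failure, 3 months | Failure, 12 months | Difference (points) | Share of 12-month failures that are later events |
|---|---|---|---|---|---|
| 2% | 2% | 2.49% | 3.94% | 1.45 | 49% |
| 2% | 5% | 3.22% | 6.78% | 3.56 | 70% |
| 5% | 2% | 5.47% | 6.88% | 1.41 | 27% |
| 5% | 5% | 6.18% | 9.63% | 3.45 | 48% |

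The last column is (failure at 12 months − p) / failure at 12 months.

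**4. Effect on the pooled rate.** If a share w of patients has a first scan at 12 months and the rest at 3 months, the pooled failure rate rises by w × difference. With w = 20% (also an assumption), that is 0.20 × 1.41 = 0.28 to 0.20 × 3.56 = 0.71 points. The documents do not give w.

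**5. How much a time limit removes.** The later events included by time t are (1 − p) × (1 − exp(−h × t)). For p = 2% and h = 5%:
- day 92: 0.98 × (1 − exp(−0.05 × 92/365.25)) = 1.23 points
- day 275: 0.98 × (1 − exp(−0.05 × 275/365.25)) = 3.62 points
- 12 months: 4.78 points

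A limit at day 275 removes only part of the problem; a limit at day 92 removes most of it.

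**6. What else is planned.** SAP 8.8.1 summarises time from procedure to imaging at each visit. SAP 8.6.4 tabulates enhancing recurrence and enhancing progression by visit, including by procedure method, and SAP 8.6.9.1 tabulates lesion status by visit. These show the spread of scan times and the window-specific findings, but none is linked to technical success.

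**The case against.** The case for leaving the plan alone has several parts.

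- **It is one descriptive line.** The registry is not powered for formal analysis. Technical success is not in the efficacy list of SAP 6.4 and is not an outcome in the regression models of SAP 7.2. Its label says that it is read at the first imaging. This stands and limits the weight of the point, but the label does not tell a reader when that imaging was done.
- **No comparison is planned.** A reader might infer that sites with late scans, or one surgical approach, will be reported as technically worse. The documents do not support that: SAP 8.7.1 plans a single pooled rate, by neither site nor approach. The same dependence on timing would affect such a comparison only if someone added it.
- **The size is hypothetical.** Both rates are assumed, and the table contrasts everyone at 3 months with everyone at 12. This stands; step 4 of the working shows how far a mixture dilutes the difference.
- **Double counting.** A reader might infer that late scans make one finding count twice, because SAP 6.4.4 says: "Time to recurrence (TTR) is defined as the time from date of cryoprocedure to disease recurrence with enhancement in at least one lesion". That overlap is not specific to late scans: an enhancing Recurrent lesion on day 40 is also both a technical failure and a recurrence event. For a first scan after day 549 it disappears, because the 6 and 12 Month windows have been missed and the second censoring rule in SAP 8.6.6.1 removes the event. It is not part of this point.
- **A hard cut-off could lose events.** Counting late first scans only toward time to recurrence would drop enhancing Progressing lesions from both results, since SAP 5.2 and 6.4.4 exclude progression as a recurrence event. This stands and shapes the fix.

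**Conclusion.** The point holds as a matter of definition and reporting. SAP 6.5.1 sets no time limit on the scan that decides technical success, follow-up timing is left to each physician, and the pooled rate in SAP 8.7.1 is not tied to scan time. Followed as written, the rule can record recurrence or progression after a complete ablation as a procedural failure.

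Over the four assumed combinations, moving the first scan from 3 to 12 months adds about 1.4 to 3.6 points of apparent failure, and roughly 27% to 70% of failures at 12 months would be later events. The pooled rate shifts by that difference multiplied by the share of late first scans, which the documents do not give. If nearly all patients were scanned early, the effect would be negligible. Only enhancing lesions are affected.

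The documents support neither a claim of biased site or approach comparisons nor one of double counting. What they support is a cheap change that makes the rate interpretable.

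**What to change.** In SAP 6.5.1 and 8.7.1:

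1. Tabulate technical success by the window of first imaging, using existing boundaries: days 1–92, days 93–275, and after day 275. Give the number of patients in each window by procedure method and site.
2. Beside the as-written all-scan rate, report the rate restricted to first scans on days 1–92 and, separately, on days 1–275. The second still includes some later events (step 5 of the working), which is why both are needed.
3. State that failures on first scans after day 275 cannot be separated from later recurrence or progression.
4. Do not reassign late first scans to the time-to-recurrence analysis alone. Enhancing Progressing lesions must stay visible in the all-scan rate and in the by-visit progression table of SAP 8.6.4.

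The cost is some SAP wording and one extra table from dates already recorded, with no change to data collection or patient care. The downside is smaller denominators, and so wider uncertainty, for the time-limited rates.
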